6.1.3.1 Handling of missing values/censoring/discontinuations

The CFU counts assessed within 2 weeks after bronchiectasis exacerbations or during or after last dose of antibiotics will not be included in the primary analysis. This is because of the potential confounding effect were expected from the use of antibiotics.

However, the CFU counts at the following visits (if there is no antibiotics use and no bronchiectasis exacerbation) are assumed not to be confounded and will be included in the primary analysis.

Efficacy data collected during intake of rescue medication will be used for analysis, since no confounding effect is expected from the use of rescue medication. Of note, on days of rescue medication intake participants are instructed to fill in the e-diary for that day prior to intake of rescue medication.

Missing on-treatment data related to the primary endpoint will not be explicitly imputed. The repeated measures analysis includes all available information in terms of measurements at all times. If endpoint measurements are missing at random, an analysis of the available data provides consistent estimates of model parameters.

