**AND** 

A clinician determines that a change in bronchiectasis treatment is required (e.g. requiring systemic glucocorticosteroid treatment and/or systemic or inhaled antibiotics).

A worsening of symptoms that either does not meet the above symptom definition but is treated by the investigator with antibiotics or steroids or both, or that meets the symptom definition but is not treated with antibiotics or steroids or both, is not considered a pulmonary exacerbation for the study.

For the above reported signs and symptoms, additional information will be collected to document if the reported signs and symptoms last for more than 48 hours.

Patients should contact the site when experiencing a pulmonary exacerbation. An unscheduled visit should occur within 2 working days of the event to confirm the diagnosis, unless the patient is hospitalized and thus unable to attend the site. AEs/SAEs, concomitant medications, and safety laboratory exams should be captured, as appropriate.

The start date for a pulmonary exacerbation recorded in the CRF should be the first day of treatment with antibiotics or steroids or both, as defined above. The end of a pulmonary exacerbation episode is marked by the end of treatment with antibiotics or steroids or both.

An exacerbation might result in missed or rescheduled visit(s) and missing associated CRF data in some circumstances.

Patients who develop a pulmonary exacerbation between screening and prior to treatment will be screen failed but will be permitted to be re-screened once the inclusion/exclusion criteria have been met (see Section 5.2 Exclusion criteria).

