#### 12.4.2 Statistical model, hypothesis, and method of analysis

The primary analysis will include all available data from subjects in the PD analysis set.

The CFU counts assessed within 2 weeks after pulmonary exacerbations or during or after last dose of antibiotics other than macrolide would be set to missing if a valid unscheduled assessment did not happen at that time point for the primary analysis.

The primary endpoint will be analyzed using a Bayesian repeated measures model with change from baseline in CFU counts (on log10-transformed scale) as response, including the fixed factors and covariates but are not limited to: treatment group, visit, effect of treatment\*visit interaction, status of macrolides use at screening, and baseline CFU counts (on log10-transformed scale) by time interaction. In absence of informative data, non-informative priors for the model parameters will be used. The prior for placebo may be updated as a weakly informative prior and will be specified in the statistical analysis plan, should new relevant data become available before the database lock of this study.

A comparison of QBW251 vs. placebo is of primary interest. Based on the fitted Bayesian model for repeated measures, the posterior probability of QBW251 effect over placebo for  $log_{10}CFU$  will be calculated. Statistical evidence will be concluded if there is 90% probability that the true effect over placebo for  $log_{10}CFU$  is >0.

The posterior probabilities of efficacy will be assessed according to the following criteria:

1. **Go / success criteria** at final: Better than placebo with high confidence (at least 90% probability that the change from baseline in  $log_{10}CFU$  for QBW251 is better than placebo, i.e. Posterior Prob (delta > 0) > 0.90)

Due to the nonconfirmatory nature of this study, no multiplicity adjustment will be applied.

In addition, the mean and corresponding two-sided 80% credible interval for the QBW251 difference to placebo from the posterior distribution will be presented.

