# 12.4.3 Handling of missing values/censoring/discontinuations

Since the primary estimand is related to an effect outside of antibiotics intake, the CFU counts assessed within 2 weeks after pulmonary exacerbations or during or after last dose of antibiotics, other than macrolide, would not be included in the primary estimand. They will be excluded from the primary estimand, if a valid unscheduled assessment did not happen at the time point for the primary analysis. This is because of the potential confounding effect were expected from the use of antibiotics.

If a valid unscheduled assessment happened at the time point for the primary analysis, then the CFU data collected during the unscheduled visit will be included in the primary estimand. Details about the definition of unscheduled visit is provided in the site manual.

However, the CFU counts at the following visits (if there is no antibiotics use and no pulmonary exacerbation) are assumed not to be confounded and will be included in the primary estimand of interest.

For the primary analysis, only on-treatment data (from date of first randomized dose up to 1 day after date of last randomized dose) will be used as the estimand specifies a hypothetical on treatment effect. Missing on-treatment data related to primary endpoint will not be explicitly imputed. If endpoint measurements are missing at random, an analysis of the available data provides consistent estimates of model parameters.

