# 12.4.4 Sensitivity and Supportive analyses

The primary estimand described in Section 12.4.1 is complemented by two supplementary estimands. This would allow to assess the robustness of the QBW251 treatment effect on bacterial load drop with and without antibiotics use / pulmonary exacerbations that would be deemed to affect the outcome of interest.

- To estimate the effect of study drug versus placebo without potential confounding due to the antibiotics use for exacerbation. All visits after receiving antibiotics other than macrolide will not be included in the CFU analysis (they will be set as missing). Note that this approach will lead to less data being used than the primary estimand.
- To estimate the effect regardless of antibiotic use. This estimand follows the treatment policy strategy where antibiotics are used as needed basis on top of study treatment as in clinical practice. Thus, the CFU measurements collected during the intake of antibiotics will be included in the analysis. The estimate of treatment actually means (treatment + any antibiotics) in this context.

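### SAP 6.1.3.1 sets no end to the removal of CFU values after antibiotics and omits the protocol's macrolide exception, so as worded it does not match the primary estimand

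*SAP*

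**What the plan says.** **SAP 6.1.3.1.** CFU counts "assessed within 2 weeks after bronchiectasis exacerbations or during or after last dose of antibiotics will not be included in the primary analysis". The next paragraph lets later data back in: "the CFU counts at the following visits (if there is no antibiotics use and no bronchiectasis exacerbation) are assumed not to be confounded", and so they stay in the primary analysis. Neither sentence gives a number of days after the last antibiotic dose, and neither mentions macrolides.

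**Protocol 12.4.2 and 12.4.3.** The same rule appears, but with an exception. Counts "within 2 weeks after pulmonary exacerbations or during or after last dose of antibiotics other than macrolide would be set to missing" (12.4.2), and counts "during or after last dose of antibiotics, other than macrolide, would not be included in the primary estimand" (12.4.3). Both sections let a valid unscheduled assessment stand in for an affected one. Section 12.4.3 also limits the primary analysis to on-treatment data, up to one day after the last randomized dose.

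**Protocol 12.4.4.** The first supplementary estimand is stricter: "All visits after receiving antibiotics other than macrolide will not be included in the CFU analysis". The protocol notes that it uses less data than the primary. SAP 6.1.4 drops the supplementary analyses because of termination.

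**Protocol 8.4.4.** Exacerbations are dated at both ends. "The start date for a pulmonary exacerbation recorded in the CRF should be the first day of treatment with antibiotics or steroids or both". "The end of a pulmonary exacerbation episode is marked by the end of treatment with antibiotics or steroids or both".

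**SAP 6.1.3.** The primary comparison is now an MMRM on change in log10 CFU, with macrolide use at screening as a covariate and a two-sided 80% confidence interval. The original proof-of-concept criteria are no longer evaluated.

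**The concern.** The sentence decides which week-12 values enter the only modelled between-arm efficacy comparison left in the SAP. It is faulty in three ways.

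1. The two-week limit stands in front of the exacerbation clause. The antibiotic clause has no limit of its own, so its plain wording runs to the end of follow-up.
2. Without the macrolide exception, a patient on permitted maintenance macrolides is taking an antibiotic at every visit. The re-entry paragraph does not help, because it too requires no antibiotic use.
3. The two weeks could be counted from either exacerbation date in Protocol 8.4.4. The SAP does not cite that section.

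The choice affects the number of values and hence the width of the interval. It could also affect the estimate: the protocol hypothesises fewer exacerbations on QBW251, so removals may differ between arms. The documents give no basis for a direction or size of such a shift. With the supplementary analyses dropped, no second planned analysis would show how much the choice mattered.

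**Working it through.** **1. The texts side by side.**
- *Antibiotic clause.* If the primary rule removed everything after antibiotics, it would do what the supplementary rule in Protocol 12.4.4 does, and that rule could not use less data than the primary on this account. The SAP's re-entry paragraph would also be empty for antibiotic users. A limited window is therefore meant, but its length is not stated.
- *Macrolides.* If maintenance users were removed, macrolide use at screening would be left with essentially one level and could not serve as a covariate in SAP 6.1.3. The omission contradicts the SAP's own model as well as the protocol.
- *Where each clause acts alone.* Protocol Table 6-2 allows antibiotics for acute infections. Under 8.4.4, a worsening treated with antibiotics that misses the symptom definition is not an exacerbation. Only the clause without a limit governs these cases. Conversely, an exacerbation may be treated with steroids alone, and then only the two-week clause governs.

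**2. Example courses against the CFU visits on Days 28, 56 and 84.** Limited means during the course and for 14 days after it. Literal means everything from the first dose on.

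| Antibiotic course | Limited removes | Literal removes |
|---|---|---|
| Days 20–33 | 28 | 28, 56, 84 |
| Days 30–43 | 56 | 56, 84 |
| Days 57–63 | none (Day 84 is 84 − 63 = 21 days after) | 84 |

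For a steroid-only exacerbation on Days 60–73, Day 84 is 84 − 73 = 11 days after the end and 84 − 60 = 24 days after the start. Counting from the end removes it; counting from the start keeps it.

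**3. The plan's own figure (Protocol 12.8.1).** Difference 1.5, SD 2.8, 30 completers per arm, 10% level taken as one-sided: 1.5 / (2.8 × √(2/30)) − 1.2816 = 2.075 − 1.282 = 0.793, and Φ(0.793) = 0.786. This agrees with the stated 79%. A two-sided 10% level gives 0.666 and does not. Also 60 / (1 − 0.16) = 71.4, hence 72 randomized.

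**4. Size of the disagreement (illustration).**
- From the documents: SD 2.8, 60 completers, week 12 at Day 84.
- Assumed: constant exacerbation rate *r* in both arms; each event treated with a 14-day antibiotic course; week-12 values only, with no borrowing from earlier visits. The 1.3 to 3 per patient-year comes from the disease background in Protocol 1.1. The 0.5 is an added low value.
- Share of week-12 values removed: limited, 1 − exp(−*r* × 28/365.25), where 28 = 14 + 14; literal, 1 − exp(−*r* × 84/365.25).
- N = 60 × (1 − share); SE = 2.8 × √(4/N); 80% half-width = 1.2816 × SE.

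| *r* per year | Limited | Literal | Difference | Of 60 | Half-width, limited / literal |
|---|---|---|---|---|---|
| 0.5 | 3.8% | 10.9% | 7.1% | about 4 | 0.94 / 0.98 |
| 1.3 | 9.5% | 25.8% | 16.4% | about 10 | 0.97 / 1.08 |
| 3 | 20.5% | 49.8% | 29.3% | about 18 | 1.04 / 1.31 |

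With nothing removed, SE is 0.72 and the half-width 0.93. With 7-day courses the limited window is 21 days, and the difference becomes 18.6% at 1.3 and 34.0% at 3 per year.

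**The case against.** The strongest reply is that the documents settle the intent. The re-entry paragraph keeps later visits and Protocol 12.4.4 gives unlimited removal to another estimand, so no careful reader would program the literal rule. For a treated exacerbation, 8.4.4 ends the episode when treatment ends, so two weeks after the exacerbation is already two weeks after treatment. The open window then matters mainly for antibiotics given outside a defined exacerbation. This largely stands, and it lowers the severity. It does not supply the number of days, and it does not restore the macrolide exception.

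A reader might also infer that exacerbations have no usable dates. Protocol 8.4.4 gives both, and *after* most naturally means after the end. The gap is only that the SAP does not say so.

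The illustrative sizes are open to fair challenge. The rate is disease background. Entry requires only one exacerbation since January 2019 and stable status, so the trial rate may be lower. The SAP itself refers to a low sample size after termination (in its PK/PD section), so 60 may not describe the data analysed.

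Finally, SAP 1.1 places the SAP among documents that carry programming detail, and a definition may exist elsewhere. A reader might infer that a programmer will choose the rule after seeing the data; the documents do not say this.

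**Conclusion.** The point holds as a mismatch in wording that should be fixed, not as a fatal flaw. As written, the SAP sentence has no end after antibiotics, contradicts the paragraph that follows it, and omits an exception that the protocol states twice. The antibiotic wording is equally open in Protocol 12.4.2 and 12.4.3; the lost macrolide exception is the SAP's alone.

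A reader might conclude that the SAP has replaced the primary estimand with the supplementary one, or that the two readings are equally supported. Neither follows, because the re-entry paragraph and Protocol 12.4.4 favour a limited window.

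Under the stated assumptions (14-day courses, 60 completers, constant equal rates), the limited and literal readings differ on about 16% to 29% of week-12 values at 1.3 to 3 exacerbations per year, and on about 7% at 0.5 per year. These figures show scale and do not forecast this dataset. They exclude the macrolide omission, whose size depends on the unstated number of maintenance users. The effect falls on the MMRM estimate and its 80% interval, with no decision rule attached.

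**What to change.** Replace the exclusion sentence in SAP 6.1.3.1, before unblinding, with wording such as:

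> CFU values are excluded from the first dose of an antibiotic other than a macrolide through a stated number of days after its last dose (for example 14, matching the two-week exacerbation window), and from the start of an exacerbation through 14 days after its end, using the protocol 8.4.4 dates. Other on-treatment values, including valid unscheduled assessments under protocol 12.4.2/12.4.3, are included.

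The number of days after antibiotics is the sponsor's choice, since the documents give none for that clause; what matters is that it is fixed before unblinding. The last sentence of the replacement is needed so that the new text overrides neither the protocol's on-treatment limit nor its provision for unscheduled samples. The re-entry paragraph should carry the same macrolide exception or be deleted as redundant.

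Cost: one sentence in the SAP and a matching programming specification. No new data are needed, and no protocol amendment is proposed.

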# 12.4.1 Definition of primary endpoint(s)

The primary estimand targets the hypothetical effect as if all patients had stayed on treatment for 12 weeks and as if antibiotics other than macrolide had not been available.

- **Population**: patients are defined by the study inclusion and exclusion criteria. The protocol defines the use of allowed maintenance therapy for this target population, as well as medications that are prohibited.
- Variable: change from baseline in bacterial load as measured by the number of colony forming units (CFU/ml) of potentially pathogenic microorganisms in sputum at week 12. A log10 transformation is applied to the CFU counts before forming the change from baseline computing therefore the log ratio to baseline of the bacterial load.
- **Intervention effect** of interest:
- Intake of antibiotics other than macrolide and intake of rescue medication
- Treatment discontinuation or study participation: hypothetical on treatment CFU counts
  - Summary measure: difference in variable means (QBW251 compared with placebo)

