6.1.2 Descriptive analysis

The baseline CFU (on log10-transformed scale) of potentially pathogenic microorganisms in spontaneous sputum is defined as the bacterial load collected at baseline (on log10-transfromed scale). "No growth" means there is no growth from the sputum specimen for that visit. The maximum measurable CFU from lab culture will be set as 600,000,000. Thus, any CFU data that is higher than 600,000,000 will be considered as 600,000,000 in reporting.

In order to be included in the sputum analysis, a subject must provide a sufficient sputum sample at screening, and/or at baseline and at least one post-baseline visit.

Summary statistics will be provided by treatment group and visit for the primary variable and will include mean, standard deviation (SD), coefficient of variation (CV), median, minimum and maximum.

6.1.3 Statistical model, assumptions and hypotheses,

The planned Bayesian repeated measures model will not be performed due to study termination and in absence of informative data, the original PoC criteria will not be evaluated as well.

The primary analysis will include all available data from subjects in the PD analysis set.

Differences between treatment groups (QBW251 versus placebo) for change from baseline in CFU counts (on log10-transformed scale) will be analyzed using a mixed model for repeated measurements (MMRM). The analysis will be carried out using SAS proc mixed procedure with Unstructured covariance structure, with treatment group and visit as fixed effects, baseline log (CFU count), status of macrolides use at screening as covariates, adjusting for effect of treatment*visit, baseline value*visit. Contrasts for treatment differences will be provided together with two-sided 80% confidence intervals.

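### SAP 6.1.3.1 drops the macrolide exemption from the antibiotic exclusion, and with it the protocol's on-treatment window and unscheduled-assessment clause

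*SAP*

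**What the plan says.** **Protocol.** The primary estimand in 12.4.1 is the effect with all patients on treatment for 12 weeks and "as if antibiotics other than macrolide had not been available". Section 12.4.2 carries this into the data rule: values taken within two weeks after an exacerbation or "during or after last dose of antibiotics other than macrolide would be set to missing if a valid unscheduled assessment did not happen". Section 12.4.3 repeats that values "during or after last dose of antibiotics, other than macrolide, would not be included in the primary estimand" and adds two provisions. If there was a valid unscheduled assessment, "then the CFU data collected during the unscheduled visit will be included in the primary estimand". The second provision is a time limit: "only on-treatment data (from date of first randomized dose up to 1 day after date of last randomized dose) will be used".

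**SAP.** Section 6.1.3.1 keeps the two-week exacerbation rule but then says that values "during or after last dose of antibiotics will not be included in the primary analysis", with no mention of macrolides. Later visits come back in "if there is no antibiotics use and no bronchiectasis exacerbation". Neither the unscheduled-assessment provision nor the one-day window appears. The model in SAP 6.1.3 nevertheless adjusts for "status of macrolides use at screening as covariates".

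**The concern.** The protocol treats macrolides as a kind of antibiotic. Section 4.5 calls them antibiotics, exclusion criterion 24 in 5.2 exempts chronic macrolides from its antibiotic exclusion, and Table 6-2 lists them as an exception within the antibiotics row. Section 3.1 has patients already taking them continue at the same dose and regimen during the study. A rule that removes CFU values taken under any antibiotic therefore reaches every visit of such a patient.

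The primary contrast would then apply to macrolide non-users only, although macrolide use is permitted background therapy and a randomization stratification factor (Protocol 6.3.2). SAP 6.1.4 cancels the supportive analyses, so no other planned model would bring these values back. Two programmers could also derive the exclusion flag differently, each with text to support the choice.

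The other two omissions matter less but come from the same rule. Without the window, CFU values taken after study drug has stopped are not ruled out. Without the unscheduled-assessment clause, values that the protocol would use are lost.

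**Working it through.** **1. Texts compared**

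| Element | Protocol 12.4.1 to 12.4.3 | SAP 6.1.3.1 |
|---|---|---|
| Antibiotics that trigger exclusion | All except macrolides | All |
| Return of later visits | No antibiotic use, no exacerbation | Same condition |
| Valid unscheduled assessment | Used in place of the affected value | Not mentioned |
| On-treatment window | First dose to 1 day after last dose | Not defined |

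The protocol's return condition does not name macrolides either. It does no harm there, because macrolide-period values were never excluded. In the SAP they are excluded, so the same condition keeps them out.

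SAP 6.1.3.1 mentions missing on-treatment data but does not define the term. The only on-treatment period the SAP defines is the adverse-event one in 7.2, which runs to 1 week after last dose.

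**2. Is it a declared change?** SAP 1.1 and 1.2 say that the SAP implements protocol v03. Departures due to termination are labelled as such (the Bayesian model and proof-of-concept criteria in 6.1.3, the supportive analyses in 6.1.4, the secondary models). Section 6.1.3.1 gives no such reason.

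**3. Planning figure.** Inputs from Protocol 12.8.1: difference 1.5, SD 2.8 (both log10 CFU), 30 completers per arm, 10% level. The level is taken as one-sided, which matches the stated 10% chance of a false positive.

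Power = Φ(1.5 / (2.8·√(2/30)) − 1.2816) = Φ(2.075 − 1.282) = 0.786.

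This reproduces the stated 79%, so SD 2.8 and 30 per arm are a sound base for illustration.

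**4. Loss of precision under the literal reading.** Let p be the share of patients whose CFU values are all removed, taken as equal in the two arms. The width of the 80% interval is multiplied by 1/√(1−p):

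| p (assumed) | Width ratio |
|---|---|
| 0.10 | 1.054 |
| 0.20 | 1.118 |
| 0.30 | 1.195 |
| 0.40 | 1.291 |

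The ratio does not depend on the sample size reached. In absolute terms, half-width = 1.2816 × 2.8 × √(2/n):

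| Per arm before removal | p = 0 | p = 0.10 | p = 0.40 |
|---|---|---|---|
| 30 (planned) | 0.927 (n = 30) | 0.977 (n = 27) | 1.196 (n = 18) |
| 10 (assumed) | 1.605 (n = 10) | 1.692 (n = 9) | 2.072 (n = 6) |

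Units are log10 CFU. With t quantiles the ratios for p = 0.10 and 0.40 are 1.06 and 1.30 at 30 per arm, and 1.06 and 1.33 at 10 per arm.

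**The case against.** The best defence is that nobody would apply the rule literally. The SAP says it implements the protocol, gives the same confounding rationale, and keeps a macrolide covariate that would have one level, or nearly so, if users were removed. This is persuasive about intent. It does not make the rule correct as written, and it shows that the SAP conflicts with itself.

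Several limits on the consequence stand:

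- The rule removes CFU records, not subjects. Affected patients stay in the PD analysis set, and one who stopped the macrolide early could re-enter at a later visit.
- The exclusion covers the primary analysis only. The descriptive summaries, individual plots and table of patients with no CFU carry no antibiotic exclusion, so these data would still be reported.
- Evidence for off-treatment cultures is thin. Patients who stop drug may stay in the study (Protocol 8.5.2 and 9.1.1), but Table 8-1 appears to schedule no sputum culture at the end-of-study visit, and the documents do not show that such values exist.
- The unscheduled-assessment clause relies on a definition in the site manual, which is not available here. Table 8-1 and Protocol 8.3.1 do provide for sputum at unscheduled and exacerbation visits, so the clause can apply to real data.
- The macrolide share and the 10 per arm are assumptions. The arithmetic holds the SD constant and treats a repeated-measures model as a two-sample comparison.

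**Conclusion.** The concern holds. SAP 6.1.3.1 states a primary-analysis rule that differs from the protocol in three respects, none of them restored elsewhere in the SAP or justified by termination. The missing macrolide exemption is the main one: followed as written, continuing macrolide users contribute nothing to the only planned primary model. The cost is an 80% interval about 5% to 29% wider if 10% to 40% of patients use macrolides, and a contrast that no longer matches the protocol's population and estimand. The effect of the other two omissions cannot be sized from the documents.

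This should be corrected before the analysis is run. It is not more serious than that, because the omission is probably unintended and no go/no-go decision depends on the result.

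**What to change.** Amend SAP 6.1.3.1 to state the following:

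- CFU values within two weeks after an exacerbation, or during or after the last dose of a non-macrolide antibiotic, are set to missing unless there was a valid unscheduled assessment at that time point. If there was, its value is used.
- Values at later visits are included when there is no exacerbation and no use of non-macrolide antibiotics.
- Post-baseline values are limited to the period from first randomized dose to 1 day after last randomized dose.

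This restores Protocol 12.4.2 and 12.4.3 with two clarifications. The macrolide exemption is carried into the return condition, and the window is applied to post-baseline values so that it cannot be read as excluding baseline cultures, which Table 8-1 allows before Day 1.

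If the sponsor does intend to exclude values under macrolides, the SAP should say so, justify it, restate the target population and drop the macrolide covariate.

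The cost is SAP wording and one derivation flag. No new data are needed.
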